This is a multi-wave study, with approximately all the participants recruited by the end of Year 02 and the remainder in the beginning of Year 03. At baseline, we will conduct comprehensive assessments of all study constructs and repeat all other assessments annually. Activities during the first three months will consist of the following: Staffing, Instrument Calibration, Ethnographic Update. Each wave will be composed of 22 participants to be randomized into two groups (11 each). Each undergo assessment at intake (T1) and outtake (T2), a booster session 3 months after outtake and a final assessment at 12 months. Data analysis process will be initiated at the third month and continue throughout the study implementation.

Study Protocol

[figure not shown]
IRB ID: 20180597 (CR00012479)

Study Number: 1 R34 DA043784-01A1

Date: July 19, 2018

Publications are expected to start from month 20. The table below details the activity processes.

Project Timeline

9) Study Endpoints*

Primary outcomes are: intervention attendance and completion; sustained abstinence in substance use through biochemical verification and self-report; family functioning; sexual risk behavior; and conduct disorder.

Secondary outcomes include recidivism in delinquency, improvement in family communication, and peer/gang involvement.

10) Procedures Involved*

RCT procedures

CIFFTA has three major components – Family-Based Therapy, Individual Therapy, and Psycho-educational Modules – delivered over 16 weeks in a six sessions (60 minutes each) per month format. In this study, the therapy will be delivered in the home to reduce missed sessions and premature termination. Special training will focus on how to structure the home environment to reduce distractions. Three sessions per month will typically be a session which may include Family-based Therapy or Psycho-educational modules with the family or parents alone (e.g., parent training). The other three sessions are typically with the adolescent alone and include Motivational Interviewing or Psycho-educational modules designed for the adolescent.

Study Protocol

IRB ID: 20180597 (CR00012479)

Study Number: 1 R34 DA043784-01A1

Date: July 19, 2018

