CIFFTA uses a flexible manual that allows for tailoring of the intervention through the selection of psycho-educational modules that address specific family and adolescent clinical and cultural issues that are central to that lives of that family. Individual and family level targets of change must be specifically able to address the ecological factors as well. For example, parenting practices may be improved to better monitor the adolescent's peers; parental leadership and guidance may focus on taking a more active role in advocacy in schools and in teaching adolescents how to handle racism and discrimination; and adolescent skills may become important in better addressing peer pressure in the peer context.

Overall intervention process.

Study Protocol

IRB ID: 20180597 (CR00012479)

Study Number: 1 R34 DA043784-01A1

Date: July 19, 2018

Pretest. CIFFTA instruments only will be pretested with a subsample of 5 Haitian youths and their families. Youths and families will be selected purposefully and will NOT be included in the study sample. Because the whole trial is consist of testing the applicability of CIFFTA within this population, the study will not be tested prior implementation. The instruments will be tested for fidelity of translation.

Study Process. Randomization will be done after baseline data are logged and will be carried out via computer-generated sequential assignment; in that sense, interventionists do not control randomization and interviewees will be blind to condition. At baseline, we will conduct comprehensive assessments of all study constructs and repeat all other assessments (see timeline). Outcomes anticipated will include lowered risk for re-offending (i.e. YLS scores), rates of recidivism (i.e. re-arrest), drug/alcohol use, and improved psychological adjustment and family functioning of those youths in the intervention group relative to those in the comparison group. Similarly, we expect parents/caregivers of these youths to see improvement in their child's behavior (i.e. less conduct disorder reported) and improved family functioning overall.

Ethnography.

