### ***Analytic Methods***

Latent Growth Modeling within a Structural Equation Model (SEM) framework. We will conduct latent growth curve analyses using Stata 14 gsem (1), SAS Proc Mixed (2), SPSS Mixed Models, and/or Mplus 8 (3) to compare the trajectories of participants in CIFFTA to those in TAU. Given that the data are balanced and have more than 2 time points, the model is identified, thereby allowing us to perform SEM growth curve analysis (4). These models conceptualize each component of growth (the baseline/intercept, the slope/rate of change, the quadratic slope, etc.) as composed of a fixed and random effect. Thus, these models have multiple components of variance as well as a regression-type model of the underlying mean growth curves of the two groups. Within an SEM framework, growth curves are treated as latent (unobserved) variables influenced by occasion- and individual-level covariates, allowing us to explicitly model growth trajectories overtime.

Specific analysis link functions will be matched to fit the distribution of each outcome variable. For ordinal outcomes (e.g., frequency of drug/alcohol usage), we will use an ordinal logistic regression function. The proportional odds assumption will be evaluated using the Brant test, and if needed, addressed by allowing problematic coefficients to vary across levels of the outcome variable. Count outcome measures (e.g., number of sexual partners, problem behaviors, re-arrests) will be analyzed using a negative binomial function rather than Poisson regression to address potential over-dispersion. Vuong tests will be performed to assess whether the data have an excess of zeros, and if necessary, zero inflated negative binomial regression will be used instead.

Analysis for Aims 2 and 3: The first set of analyses will explore the efficacy of CIFFTA compared to SOC in modifying the main adolescent outcomes and to generate effect sizes for a possible full clinical trial: a) drug/alcohol use, b) risky sexual behavior, c) delinquent behavior, and d) recidivism. Latent growth modeling will be used to investigate the efficacy of CIFFTA as compared to SOC. For each model, we will examine the effect sizes to determine the overall impact of CIFFTA over SOC on the outcome variables. We will generate estimates of effect sizes, such as Cohen's d (5), for both rate of change and for the

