**Power Analysis:** We will recruit 88 participants for this study, with the intention of analyzing data for 80 participants after attrition. The original CIFFTA randomized trial with 28 Hispanic adolescents showed CIFFTA to be more efficacious than the comparison family treatment at: 1) reducing drug use, and 2) improving parenting practices as reported by adolescents (7). More recently, a technology assisted CIFFTA study of 80 minority youth at high risk for drug use showed CIFFTA to be more efficacious in reducing behavior and conduct problems and in improving family cohesion, when compared to a delay treatment condition (8). Based on these findings, CIFFTA was placed on the National Registry of Evidence Based Practices using their more rigorous criteria for entry. Given such consistent findings of efficacy for CIFFTA among Hispanic youth, a sample size of 80 will be sufficiently powerful to detect relatively small effects ( $R^2 = 0.05$ ) at adequate levels of power (0.84 - 0.86) using a relatively simple SEM. A sample size of 80 is also well above sample guidelines for Stage 1 treatment trials (80)). Nevertheless, to deal with attrition, which in the case of Haitian and because of the ethnographer's engagement with the families will not be higher than 10%, we plan a sample of 88 adolescents.

Nevertheless, we recognize and appreciate the limits of estimating simple SEMs, such as ours, with a small sample size. Therefore, we will take several steps to mitigate concerns about statistical power, including: limiting the use of latent variables when possible, constructing parsimonious path models, and using Bayesian estimators. When theoretically and empirically appropriate, we will use principal components factor analysis to combine multiple indicators into a single scale capturing the underlying construct rather than estimating multiple latent variables since the latter often requires larger samples.

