Survival analyses can also be performed within a SEM framework. We will utilize shared frailty proportional hazard Cox regression as it does not make assumptions about the baseline hazard rate like other survival analyses (e.g., exponential, Weibull), while the shared frailty component of the model will allow us to adjust for the dependence of survival times via random effects (12). Survival analysis is ideal for estimating time-to-event data such as the hazard rate of drug/alcohol use and sexual risk behavior during the post-intervention phase. Because our study contains 4 waves, each with their own start/finish date, the data will be right-censored, thereby necessitating the use of survival analysis techniques. While ordinary least squares regression treats censored cases as missing, survival analysis will adjust for censoring when calculating hazard rates, providing more accurate estimates (12).

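### Youths are allocated 11:11 within four waves, but no SAP model names wave; if outcomes differ by wave, linear comparisons at a given time point are mildly conservative

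*Protocol*

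**What the plan says.** Protocol section 8 (Study Timelines) describes a multi-wave study: "Each wave will be composed of 22 participants to be randomized into two groups (11 each". In Protocol section 10, under Study Process, randomisation follows the logging of baseline data and "will be carried out via computer-generated sequential assignment"; wave is not mentioned there.

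The SAP's Power Analysis states "We will recruit 88 participants for this study, with the intention of analyzing data for 80 participants after attrition". On efficacy, its Analytic Methods section says "Latent growth modeling will be used to investigate the efficacy of CIFFTA as compared to SOC". It plans effect sizes both for the rate of change and for the difference between arms at a given time. Mediation models and shared-frailty Cox models follow.

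In the SAP text available, waves appear once, in the survival part of Analysis Rationale: "Because our study contains 4 waves, each with their own start/finish date, the data will be right-censored". Wave is not named as a covariate, stratum or random effect in the growth, mediation or Cox models. The list of methods in Protocol section 12, which includes analysis of variance and logistic regression, does not name it either.

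**The concern.** An exact 11:11 split in every wave cannot be guaranteed by simple randomisation. It needs allocation restricted within wave, and the usual principle is that the analysis reflects such a restriction. Balance within wave already removes wave differences from the treatment contrast. A linear model without wave still counts those differences as residual variance, so the test rejects too rarely under the null and gives up some power.

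The waves run at different calendar times, so differences between them are plausible, though the documents do not show any. The SAP itself lists steps to ease its concern about power in a small sample, and its effect sizes are meant to inform a full trial. Naming wave would fit on that list.

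**Working it through.** **Inputs.** 22 youths per wave, 11:11 (Protocol section 8). Four waves (SAP, Analysis Rationale), consistent with 88/22 = 4. 80 analysed (SAP, Power Analysis), so 80/8 = 10 per arm per wave if attrition is even. The documents give no alpha, so two-sided 0.05 is assumed. They give no between-wave variance, so its share ρ of total variance is assumed over 0 to 0.20.

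**The plan's own power figure.** The SAP claims to detect "relatively small effects ( $R^2 = 0.05$ ) at adequate levels of power (0.84 - 0.86") with 80 youths. For one tested parameter, f² = 0.05/0.95 = 0.0526 and λ = 80 × 0.0526 = 4.21. The noncentral F test on 1 and 78 degrees of freedom then gives power 0.53. The stated figure is not reproduced; that is a separate matter, taken up under the verdict only as far as it touches wave. The equivalent standardised difference is d = 2√0.0526 = 0.459.

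**Size of the standard-error inflation (linear model, one time point).** Set total variance to 1, with wave variance ρ and residual variance 1 − ρ.

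- True variance of the difference in means: (1 − ρ)(1/40 + 1/40) = (1 − ρ)/20. The wave effects cancel.
- Expected pooled variance when wave is omitted: within each arm, four waves of 10 add 10 × 3 × ρ = 30ρ to a sum of squares on 39 degrees of freedom. This gives (1 − ρ) + (30/39)ρ.
- Ratio of standard errors, omitted to included: √[1 + 0.769ρ/(1 − ρ)].
- ρ = 0.05: √1.0405 = 1.020. ρ = 0.10: √1.0855 = 1.042. ρ = 0.15: √1.1357 = 1.066. ρ = 0.20: √1.1923 = 1.092.

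Simulation (20,000 trials per setting) gave 1.021, 1.042, 1.066 and 1.091, which agrees.

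**Type I error and power at d = 0.5** (100,000 simulated trials per setting, 4 waves of 10:10):

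| Wave share ρ | Type I error, wave omitted | Power, wave omitted | Power, wave included |
|---|---|---|---|
| 0% | about 5% | 59.9% | 59.9% |
| 5% | 4.6% | 60.2% | 61.7% |
| 10% | 4.1% | 61.5% | 64.6% |
| 15% | 3.7% | 62.1% | 66.8% |

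At ρ = 2% the gain is about 0.5 point. With wave included, type I error stays at about 5% throughout.

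**Slope contrast.** With four equally spaced time points, wave as a pure level shift and one slope per youth (6,000 trials per setting), the standard error without and with wave was the same: 0.0802, 0.0772 and 0.0738 at wave variances of 0.05, 0.10 and 0.15. Power without and with wave was 45.7/45.7%, 48.0/47.8% and 51.8/51.7%. Change scores likewise gained nothing.

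**Logistic check** (6,000 trials per setting, log-odds effect −1.0, ρ = 0.10). The standard error was smaller without wave (0.489 against 0.521). The estimate was pulled toward zero (−0.99 against −1.09), and power was 0.533 without wave and 0.556 with it. Count, ordinal and Cox models were not simulated.

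**The case against.** The strongest objection is that the calculation for a single time point is not the SAP's main analysis. Latent growth modelling is, and one of its two reported effects is the rate of change. A stable wave difference sits in the intercept and cancels from slopes and change scores. This stands: the slope simulation shows no loss, and there would be one only if waves also differed in slope. It does not dispose of the point, because the SAP also plans to estimate the difference between arms at a given time. Baseline adjustment would remove part of a stable shift there too.

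Second, a reader might infer that standard errors are too wide and power is lost as a matter of fact, in every model. The documents do not support that. They give no wave variance, and all youths come from one county and one referral agency under common eligibility rules, so the differences may be small. Many outcomes are ordinal, counts or times to event, where the linear mechanism does not carry over.

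Third, a reader might infer that no model contains wave. The documents show only that none names it. Covariates in the growth models are left generic, and the grouping unit of the Cox frailty is not stated. Blocking itself is read from Protocol section 8; the description in section 10 neither confirms nor contradicts it.

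Fourth, putting three indicators into every equation would be costly. An intercept, a slope and three mediators make five equations, so up to 5 × 3 = 15 extra paths with about 80 youths, against the SAP's commitment to parsimonious models. This stands, and it limits where wave should enter.

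**Conclusion.** The point holds in a limited form. Allocation is described as balanced within four waves, and no SAP model names wave. If outcomes differ by wave, linear comparisons at a given time point are conservative. At an assumed wave share of 5%, 10% or 15%, the loss is about 1.5, 3 or 5 power points at d = 0.5. At 2% it is about half a point, and at 0% nothing. These figures assume 10 youths per arm per wave, two-sided 0.05, no baseline adjustment, and allocation that is in fact blocked by wave. Without blocking, the type I error figures would not apply.

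A reader might also infer that the missing wave term explains why the stated power of 0.84–0.86 cannot be reproduced. It does not: at d = 0.459 and a wave share of 20%, including wave raises power only from 0.550 to 0.619.

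Any error in the linear case is on the cautious side, in a pilot that the SAP itself calls preliminary. Severity is low.

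**What to change.** In the protocol, confirm that the computer-generated sequence is blocked by wave. Add to the SAP:

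> Efficacy growth models include wave (three indicators) as a predictor of the intercept, or of the outcome in single-timepoint comparisons. Cox models are stratified by wave, and the frailty unit is named. Wave need not be added to every mediator path.

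The cost is a sentence in the protocol, a short addition to the SAP, and three degrees of freedom per efficacy model (78 to 75 residual in the simple linear comparison). In the linear simulations there was no measurable loss of power when waves did not differ.

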Eighty-eight (88) adolescents aged 13 to17 and their families will be recruited into the study to obtain 80 after attrition. Age, place of residence (Miami-Dade), and Haitian ancestry will constitute the main criteria for selection. Other criteria of inclusion are: adolescents that are NOT incarcerated and with no prior mental health care or history of psychoactive medication, to increase the homogeneity of the sample in terms of a naive population; adolescents in families who have lived in the US for 3 years, to avoid confounding initial culture shock with other conventional aspects of maladjustment; families with a range of organizational structures (nuclear and non-nuclear), to achieve variability and observe differences in family dynamics with regard to response to the intervention. Youths with a documented history of mental retardation and/or organic dysfunction will be excluded; the youths in question will be referred to appropriate agencies.

6) Number of Subjects*

Eighty-eight (88) participants will be recruited into the study. Instruments for the intervention will be pretested with 10 Haitian youth.

7) Study-Wide Recruitment Methods*

This project’s recruitment approach will consist of the following steps: (a) after initial referral by the JSD, potential participants will be approached by the ethnographer who will describe the scope of the study and ask the participant if

Study Protocol

IRB ID: 20180597 (CR00012479)

Study Number: 1 R34 DA043784-01A1

Date: July 19, 2018

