Focus Group. Focus groups will be guided by the following criteria: (a) they will be homogeneous with regard to age (parents or adolescents only); (b) they will follow a relatively structured interview guide with high involvement of the ethnographer as moderator; and (c) they will have six to ten participants each. Topical areas for the focus group will include the following: impact of the interventions; behavior changes of adolescents of parents; changes in the family.

Instrumentation.

The primary constructs for the youth participants will include: risk for re-offending, criminal history, patterns of drug/alcohol use, psychological adjustment, evidence of conduct disorder, family functioning, and acculturation. Constructs for the caregiver(s) will include their assessment of their child's conduct, family functioning, and their own level of acculturation. At baseline, information will also be gathered on participants demographic status. The instrument will be administered at participants' homes. Along with the demographic data, the baseline questionnaire will incorporate measures from the instruments described below, culminating in a unified tool taking no more than one hour to administer.

Behavioral, emotional, and academic functioning. We will administer standardized measures of youths' emotional and behavior disorders. Parent and youth reports on the Achenbach System of Empirically Based Assessment will assess youth's behavioral, emotional, and academic functioning. Parents will complete the Child Behavior Checklist (Achenbach 1983); and youth also will complete the parallel Youth Report Form (YRF). These measures yield scores for internalizing and externalizing problems and academic competence, and have DSM-5 scales for multiple problem areas: depression, anxiety, somatic, attention deficit/hyperactivity, oppositional, and conduct problems.

Risk for re-offending. Level of risk will be assessed with the Youth Level of Service/Case Management Inventory (YLS/CMI) developed by Hoge and Andrews (51) that screens for risk in eight domains (conduct disorder,

Study Protocol

IRB ID: 20180597 (CR00012479)

Study Number: 1 R34 DA043784-01A1

Date: July 19, 2018

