based research in the Haitian community in Miami-Dade. All research clinical staffs have been performing CIFFTA in diverse ethnic contexts in Miami-Dade for over two decades. They are well-trained in human subject protection and research implementation. They are well-informed of their tasks and duties and they will be trained for this study to be implemented in the Haitian community. The 88 at-risk youth (ages 13-16) of Haitian descent will be recruited in Miami-Dade County with the intention to analyze 80 participants because of attrition. Sample sizes are derived from power calculations based on data from published work.

Two therapists will deliver the CIFFTA intervention. Therapist will have experience in working with adolescents with behavior problems and with Haitian families. The first phase of therapist CIFFTA training will consist of a 3-day training workshop that includes the use of didactic material, the intervention manual, and the presentation of videotaped sessions from our previous CIFFTA work. This workshop will also include presentations by the PI and [name] on what is known about Haitian families in our community. The second phase will include intervention implementation with 1 pilot case. A therapist is required to work with a pilot case over at least a one-month period and work with that pilot cases will be supervised directly by the study PI, the CIFFTA Developer, and the CIFFTA supervisor. Because the implementation of the psycho-educational modules is fairly straightforward, training and certification efforts will focus primarily on the individual and family-based therapy components. Any rating below "adequacy" will require retraining on that specific component.

Interventions will be delivered over a briefer period than is typical of the actual intervention in the trial but will be sufficient to ensure comfort and competence in the key intervention components. There will be a 2 day workshop following the pilot phase to solidify any issues that remain and to incorporate any manual clarification that will assist in achieving high levels of competence and fidelity/adherence. This training format has been utilized successfully in our family training institute. SOC therapists will already be experienced in delivering the community standard and will not require additional training.

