difference at a particular time between the two conditions (6). Following Cohen's guidelines (5), we will interpret our effect sizes using the convention of "small" ( $d = .2$ ), "medium" ( $d = .5$ ), and "large" ( $d = .8$ ).

Our hypotheses concerning the direct and indirect effects of key variables on drugs/alcohol use, risky sexual behavior, delinquent behavior, and recidivism will be tested using SEM mediation analyses. To test potential indirect relationships we will include several mediators, including family connectedness, acculturation (bicultural involvement scale), and motivation to change. This will allow us to examine whether CIFFTA directly effects our outcomes of interest and/or whether the effect of CIFFTA operates through its effect on family connectedness, acculturation, and motivation to change. These mediation models will enable us to address **Specific Aim #2** by testing the significance of paths in the model linking the intervention variable to the risk-related outcomes in question (both at discrete points in time and as the change index derived from differences in ordinal frequency at baseline and at post-intervention time intervals).

In a separate set of analyses, we will examine the hazard rate of drug/alcohol use and sexual risk behavior during the post-intervention phase of the study. Comparisons across the two intervention conditions will thus be made regarding the hazard rate of having sex during the post-intervention period, sex with multiple partners ( $>1$  per month), and unprotected sexual episodes. Specifically, shared frailty Cox proportional hazard regression will be utilized to examine possible differences in the hazard rate of various risky behaviors (drug- and sex-related) in CIFFTA and control conditions during the post-intervention phase. This will prove particularly helpful in determining the hazard rate for post-intervention sexual initiation or unprotected sex in the two groups being compared, while also controlling for the time-dependence nature of our data. Similar analyses will be performed regarding initiation into drug use and other problem behaviors to determine whether the possible benefits of the CIFFTA approach extend to a range of risky behaviors.

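### The hazard comparisons of sexual and drug-use initiation name no baseline covariate, although age is known for every youth before randomisation; an age term should be pre-specified, for a gain that is probably modest

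*Protocol*

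**What the plan says.** Protocol section 5 (Inclusion and Exclusion Criteria): "Age, place of residence (Miami-Dade), and Haitian ancestry will constitute the main criteria for selection". Protocol section 10 (Instrumentation): "At baseline, information will also be gathered on participants demographic status". The Study Process paragraph of section 10 places randomisation after baseline data are logged, by a computer-generated sequence, and mentions no stratification by age.

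SAP, Analytic Methods: "shared frailty Cox proportional hazard regression will be utilized to examine possible differences in the hazard rate of various risky behaviors". The stated uses include "determining the hazard rate for post-intervention sexual initiation or unprotected sex in the two groups being compared", and then "Similar analyses will be performed regarding initiation into drug use and other problem behaviors". The only control mentioned there is the clause "while also controlling for the time-dependence nature of our data". The Analysis Rationale adds that the frailty part adjusts, through random effects, for dependence among survival times; it does not say what unit shares a frailty. Individual-level covariates are mentioned only for the growth curves, and none is listed.

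The age range is stated in two ways. Section 5 of the protocol has "Eighty-eight (88) adolescents aged 13 to17 and their families will be recruited into the study to obtain 80 after attrition"; section 22 (Resources Available) has "The 88 at-risk youth (ages 13-16) of Haitian descent will be recruited in Miami-Dade County".

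**The concern.** In a comparison of time to first sex or first drug use, everyone in the risk set starts from the same point: not yet begun. No baseline value of the outcome exists to explain why some youths start sooner than others. Age is recorded, fixed before allocation, and a plausible predictor of starting.

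In a Cox model, omitting a prognostic covariate moves the treatment hazard ratio toward 1 and costs power, even when the arms are balanced. If they are unbalanced on age by chance, the difference stays in the reported effect. The trial is meant to supply effect sizes for a possible full trial (SAP, Analytic Methods), so an attenuated or age-shifted hazard ratio would feed into that design. An open covariate set also allows the choice of adjustment to be made after the results are seen.

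**Working it through.** **The plan's own figure.** The SAP gives no power, event count or hazard ratio for these comparisons. Its one power figure (0.84 to 0.86, N = 80, R² = 0.05) is for a simple SEM. With f² = 0.05/0.95 = 0.0526, a two-sided 5% F test on 1 degree of freedom has power 0.53. That mismatch is a separate matter and is not used here.

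**Inputs from the documents.** 88 recruited and 80 analysed; two groups of 11 per wave, so 1:1; ages 13–17 (or 13–16).

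**Assumptions, because the documents are silent.** True treatment hazard ratio 0.5; two-sided 5% test; 80 or 40 youths at risk; 30%, 50% or 70% with an event; age hazard ratio per year 1.0, 1.25, 1.5 or 2.0.

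**Step 1, power without age.** Schoenfeld's formula is power = Φ(½·√d·|ln HR| − 1.96), with d events. For d = 40: ½ × 6.325 × 0.693 − 1.96 = 0.23, so power is 0.59. For 12, 24 and 56 events it is 0.22, 0.40 and 0.74. Power of 80% needs 66 events, which is 66/80 = 83% of all analysed youths.

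**Step 2, simulation with and without age.** Exponential times, administrative censoring, ages 13 to 17 equally likely, a plain Cox model with arm alone and with arm plus linear age, 2,500 runs per setting. The Monte Carlo standard error of each power is at most √(0.25/2500) = 0.01. Entries are power without → with age.

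| At risk, events | age HR 1.0 | 1.25 | 1.5 | 2.0 |
|---|---|---|---|---|
| 80, 30% | 0.351 → 0.356 | 0.353 → 0.364 | 0.335 → 0.372 | 0.274 → 0.351 |
| 80, 50% | 0.574 → 0.570 | 0.544 → 0.577 | 0.511 → 0.579 | 0.352 → 0.554 |
| 80, 70% | 0.724 → 0.720 | 0.686 → 0.720 | 0.596 → 0.720 | 0.410 → 0.733 |
| 40, 30% | 0.164 → 0.171 | 0.156 → 0.165 | 0.150 → 0.166 | 0.110 → 0.175 |

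For an age hazard ratio of 1.25 to 1.5 with 30% to 50% events, the gain is about 1 to 7 points. With no age effect it is nil within simulation error.

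**Step 3, weaker age effects.** With 50 at risk and log-hazard slopes of 0.1 and 0.2 per year (hazard ratios 1.11 and 1.22), power goes from 0.36 to 0.37 and from 0.35 to 0.36 at a 12-month risk of 0.6. At a risk of 0.4 it goes from 0.23 to 0.23 and from 0.22 to 0.23. Allowing for rounding, the gain is 0 to 2 points.

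**Step 4, attenuation.** With 80 at risk, 50% events and age hazard ratio 1.5, the median log hazard ratio is −0.647 without age and −0.706 with it: exp(−0.647) = 0.52 against exp(−0.706) = 0.49. At age hazard ratio 2.0 it is exp(−0.508) = 0.60 against exp(−0.691) = 0.50.

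**Step 5, cost.** For age hazard ratios up to 1.5 the standard error mostly rises by about 1% to 2.5% (0.326 to 0.331 is 1.5%; 0.613 to 0.628 is 2.4%). The largest rise in any setting is 0.271 to 0.281, or 3.7%, where the power gain is also largest. Type I error at N = 80 was 0.052–0.054 without age and 0.056–0.057 with it.

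**Step 6, chance imbalance.** For ages uniform from 13 to the 18th birthday, SD = 5/√12 = 1.44. The standard error of the arm difference is 1.44 × √(4/n), which is 0.41 for n = 50 and 0.32 for n = 80. A gap of half a year or more then has probability 22% or 12%. For 13–16, SD = 4/√12 = 1.15 and the probabilities are 13% and 5%.

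**The case against.** The SAP does not rule age out. A reader might infer from the time-dependence clause that the hazard models control for nothing else. The documents do not support that: the clause is a passing remark on the merits of the method, the model also has a frailty term, and the covariate set is simply left open. This stands. The gap is one of specification. The frailty term does not close it for initiation, because its grouping unit is undefined and one first event per youth gives it little to work with.

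The gain depends on assumed age effects. Slopes of 0.3 to 0.7 per year imply a hazard 3.3 to 16 times higher at 17 than at 13 (exp(1.2) and exp(2.8)). If age is that strong, many older youths will already have started and cannot be at risk. In an illustration with risk beginning at 11 and a 12-month risk of 0.4, this cut the age SD to about 1.2 and the gain to 2–4 points, against 2–7 without such depletion. In another setting (slope 0.5, risk 0.6, 50 at risk), tilting the risk set toward younger youths still left 0.29 → 0.39. The objection therefore limits the size but does not remove the point.

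Chance imbalance is not bias: unadjusted type I error is near 5% at N = 80, and the simulated powers already contain the imbalance, so it must not be counted again. This stands too.

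These are secondary, preliminary analyses in a plan that stresses parsimony, and other baseline predictors exist. That argues for a single pre-specified term.

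**Conclusion.** The point holds as a cheap improvement to the hazard models for initiation endpoints. The plan has age for every youth and names no baseline covariate. If age predicts starting, omitting it attenuates the hazard ratio and loses some power; if it does not, including it loses almost nothing.

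At an assumed hazard ratio of 0.5 the gain is nil with no age effect, about 0–2 points for weak effects, and about 1–7 points for 1.25–1.5 per year with 30%–50% events. It reaches 12 points at 1.5 with 70% events and 32 points at 2.0 with 70% events. The documents supply none of these inputs.

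Three stronger readings are not supported:
- **That an age term would make these comparisons well powered.** Adjusted power stays at or below 0.73 in every setting in the table, and at or below 0.18 with 40 at risk and 30% events.
- **That it is free.** It uses a parameter, slightly widens the standard error and changes the hazard ratio to one conditional on age.
- **That the same argument covers the growth-curve models.** The absence of a baseline outcome value applies only to initiation, and the SAP already allows individual-level covariates in those models.

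**What to change.** In the hazard-analysis paragraph of the SAP's Analytic Methods, add that every between-arm hazard model for an initiation endpoint includes age at randomisation, continuous in years, as a pre-specified covariate. State that the age-adjusted hazard ratio is the main result, that the unadjusted one is reported beside it, and that the adjusted hazard ratio is conditional on age.

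Reconcile the two age ranges in protocol sections 5 and 22, since the spread of ages determines both the likely gain and the chance of imbalance.

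The cost is a few sentences in the SAP, one model parameter and the small rise in standard error shown above. No new data are needed.
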